## 3. Study design and study design rationale

#### 3.1. Study design

This is a randomised, multicentre, double-blind, placebo-controlled, parallel-arm phase II/III study to assess the safety and tolerability of a single dose of acoziborole compared with placebo in adolescent and adult subjects seropositive to human African trypanosomiasis due to *T.b. gambiense* (g-HAT positive; not confirmed parasitologically [no demonstration of the parasite in any body fluid via microscopy]) in DRC and Guinea.

The double-blind, placebo-controlled nature of the study design will aid with minimising bias with the parallel-arm design allowing between subject comparison.

Subjects will be hospitalised at least 1 day before study treatment commences and will be randomised in a 3:1 ratio to acoziborole or matched placebo on Day 1 of the study. Following hospitalisation, subjects will attend follow-up visits at the study centre at 1- and 4-months post-treatment. At months 2 and 3, investigator contacts will be established between the site and subjects to ensure close follow-up of subjects and encourage study adherence. An on-site unscheduled visit will be proposed if deemed necessary by the investigator. Any subject with a positive parasitological test result during the study will end their participation in the study and be referred to the NSSCP for appropriate standard treatment.

In addition, a sub-study 'TrypSkin' to assess the presence of extravascular dermal *T.b. gambiense* in this population, will be proposed to subjects having given their consent to participate in the seropositive safety main study (in clinical sites participating in the sub-study only). Subjects can decide whether to participate or not in the sub-study independently of his/her participation in the main safety study.

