#### 8.3.2. Parasitology assessments

Assessments for presence of parasites using mAECT or mAECT-BC will be conducted during screening period, at Month 1, and at the EoS visit at Month 4. The most sensitive parasitological test (m-AECT-BC technique [16]) will be preferred to detect the presence of trypanosomes in blood. When indicated, lymph node aspirate will also be used to

microscopically detect the presence of trypanosomes.

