## 8.5.4. Eliciting adverse event information

The investigator is required to report all directly observed AEs and all AEs spontaneously reported by the trial subject using concise medical terminology. In addition, to avoid bias in eliciting AEs, each trial subject will be questioned about the occurrence of AEs during hospitalisation period and study follow-up visits, with general, non-leading questions such as *"Since xxx (e.g. last visit) have you had any health problem?"* or *"How are you feeling?"* 

All AEs (serious and non-serious) must be recorded on the source documents and CRFs regardless of the assumption of a causal relationship with the study drug(s). The definition, reporting period, and reporting requirements for AEs are described respectively in sections 8.5.1, 8.5.5 and 8.5.8).

Information on AEs must be evaluated by a physician.

Each AE is to be classified by the investigator as serious or non-serious (see definition of a SAE in section 8.5.3). This classification will determine the reporting procedure for the event.

In addition, the frequency, seriousness (see section 8.5.3), severity (see section 8.5.6), and causality (see section 8.5.7) assessment of AEs will be described.

Non-serious AEs are to be reported in the CRF, including description of the event, onset date, duration, severity, seriousness, relationship to all study drugs, actions taken and outcome.

In the CRF, a given AE will be recorded only once per subject, and the severity recorded will be the maximum level reached. If several distinct episodes of the same condition occur, their number will be recorded in the CRF.

SAEs will be reported both on the AE page of the CRF and the SAE forms.

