The AE can occur in both periods for the same subject (i.e. the event is still present at the second time period). However, for the period analysis the AE start date will be used to identify AEs in each period. The denominator of occurrence rate in each period will respectively be the number of subjects who receive at least one tablet of study treatment during the first time period and the number of subjects attending the 4-month visit or have reported a TEAE during the second time period. All statistics will be provided per time period to separately assess and interpret early events probably attributed to study treatment and late events that could be attributed to the disease or are persistent.

The time course of treatment effect will be analysed using the log rank test stratified by study centre and will be performed on the time to occurrence of TEAEs, taking into account the attrition rate of subjects who are being followed up. A loss to follow-up or a withdrawal will be censored at the time of the last attended visit. The Kaplan-Meier estimates of the proportion of subjects without any TEAE in each treatment group will be presented graphically to assess the time course of the response.

The hierarchy of testing reflects the sequence of testing from the more general effect to the most specific effect. There is a multiplicity of testing issue and an inflation of type I error that cannot be discarded. However, no adjustments of type I error are planned for this study as this study has been designed to detect any potential safety issues rather than confirming and investigating a safety concern.

The rate of occurrence of AEs will be analysed by the true positive status (subjects with parasites detected during the follow up period) in either treatment or placebo groups.

The rate of conversion to parasite positive and the rate of return to seronegative over 4 months will be analysed descriptively using frequency and proportion by treatment group.

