2.4.3. Ratio determination

Operational properties of various allocation ratios for the following assumptions are as follows:

- 1. Total sample size (for safety main study): n=1200, (900 acoziborole and 300 placebo)
- 2. Excess rate of 1% (acoziborole = 2% of AEs of interest, Placebo = 1%) for safety purposes
- 3. Probability to detect an infrequent AE ($\leq 1\%$ upper limit of class)
- 4. Probability to detect an infrequent AE (0.5% mid-class)
- 5. Total sample size (TrypSkin exploratory sub-study): n=700
- 6. Binary endpoint: Success = no tryps detected in punch skin at month 4 (failure = at least one tryp-positive result in punch skin at Month 4)
- 7. Probability to detect at least one trypanosome in derma at baseline: 20%
- 8. No effect of placebo on occurrence of tryps in derma at month 4: failure rate at 4 months = 20%
- 9. Effect of 95% of acoziborole on occurrence of tryps in derma at Month 4 (efficacy): Failure rate at Month 4 = $0.05 \times 0.20 = 0.01$ or 1%.
- **10.** Excess rate of success in acoziborole group = 19% assuming the same efficacy as stage 2 patients.

Table 2.4.3.1 presents the summary of the results for different assumptions on precision and power for the study to determine the required ratio.

	Safety			TrypSkin sub-s	TrypSkin sub-study				
Allocation ratio	Sample size for main study	Exact 95% Confidence interval limits of excess rate	Probability to detect an unfrequent AE if occurrence rate = 1% (upper limit), = 0.5% (mid-class) and = 0.1% (lower limit of class)	Sample size for sub-study	Exact 95% CI limits of excess rate Estimate = 19%	Power (chance to detect a difference vs pbo) if acoziborole efficacy is 95%			
3:1	PBO = 300 ACO = 900	Lower = -0.92% Upper = +2.41%	Upper: 99.99% Mid: 99.90% Lower: 59.36%	PBO = 175 ACO = 525	Lower = 13.38% Upper = 25.55%	99.99%			
2:1	PBO = 400 ACO = 800	Lower = -0.64 Upper = +2.42%	Upper: 99.96% Mid: 98.18% Lower: 55.06%	PBO = 233 ACO = 467	Lower =14.02% Upper = 24.62%	99.99%			
3:2	PBO = 480 ACO = 720	Lower = -2.30%* Upper = +0.66%*	Upper: 99.93% Mid: 97.29% Lower: 51.34%	PBO = 280 ACO = 420	Lower = 14.51% Upper = 24.15%	99.99%			
1:1	PBO = 600 ACO = 600	Lower = -0.44% Upper = +2.51%	Upper: 99.75% Mid: 95.06% Lower: 45.23%	PBO = 350 ACO = 350	Lower: 14.81% Upper: 23.48%	99.99%			

*Not comparable with other allocation ratio due to decimal digits in the number of subjects requiring rounding to the closest entire number

Conclusions:

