5.1. Primary Objective Analysis

The assessment of the safety of a single dose of acoziborole compared to placebo during a follow up period of 4 months will be conducted using excess rate (ER) of occurrence of any TEAE over the first 4 months in the acoziborole group compared to placebo. The numerator of the occurrence rate will be the number of subjects with at least one TEAE and the denominator will be the number of subjects in the Safety Set. In addition, a sensitivity analysis will be performed on safety set population excluding subjects with treatment misallocation. The ER is the occurrence rate of any TEAE in the acoziborole group minus the occurrence rate in the placebo group. The 95% confidence interval (CI) of the excess rate will be calculated using Wilson score interval (which provides average coverage very close to 95% in all cases⁹). The excess rate (ER) of occurrence of any TEAE will be transformed to the number of subjects needed to treat (NNT) to observe one more subject with a TEAE in the acoziborole group compared to placebo (NNT = 1 / ER).

The analysis will be performed on the total SS population and by age groups (defined as adolescents aged 15-17 years and adults aged \geq 18 years), gender, TEAE severity category and period of occurrence. Four categorizations of TEAEs per severity will be derived as 1) Serious AEs regardless of the relationship to drug, 2) severe and related to drug TEAEs and 3) mild and/or moderate regardless of relationship to drug, and 4) severe but not related to drug. TEAEs period of occurrence will be categorized as: 1) Occurrence during the hospitalization period and 2) Occurrence after the hospitalization period (from EoH to month 4). The same event for the same subject can occur at both periods (i.e., the event is still present at the second period). However, for the analysis the AE start date will be used to identify AEs in each period. The denominator of occurrence rates will be the number of subjects receiving at least one tablet of IP for the first period and the number of subjects attending the 4-month visit or having reported a TEAE during the second period.

The occurrence rate analysis will be performed on a safety set. MedDRA preferred terms of TEAE with occurrence rates ≥1% in one treatment group will be compared between treatment groups on the excess rates and NNT for any TEAE, by TEAE severity to assess whether the more severe

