events are not "diluted" in non-severe events and by period of occurrence to assess whether the late events are not "diluted" in all events.

A Cochran Mantel-Haenszel test stratified on the site of investigation will be used to compare the occurrence rate of both treatment groups. The same test will be applied to the common TEAE (>1% in any group) based on preferred terms. Generalizability of the treatment effect will be assessed using a test of homogeneity of the odds ratio (OR) across study centers. If the number of randomized subjects in each site reaches 100, then each site will be a stratum. If one or several sites had fewer than 100 subjects, then the smallest sites will be pooled together to obtain strata of at least 100 subjects. If the test of homogeneity is not significant (i.e., p-value ≥ 0.05), the combined odds ratio will be estimated as well as the 95% CI. If the hypothesis of homogeneity is rejected (i.e., p-value<0.05), then the odds ratio per site will be provided.

Time course treatment effect will be analyzed using a log rank test stratified by site and treatment group on the time to occurrence of TEAEs, considering the attrition rate of followed subjects. A loss to follow-up or a withdrawal will be censored at the time of the last attended visit. Kaplan Meier estimates of the proportion of subjects without any TEAE will be presented graphically to assess the time course of the response including results from log rank test.

The rate of occurrence of AEs will be analyzed by the true positive status (subjects with parasites detected during the follow up period) in either treatment or placebo groups.

The rate of conversion to parasite positive and the rate of return to seronegative over 4 months will be analyzed descriptively using frequency and proportion by treatment group.

There is a multiplicity of testing issue, and an inflation of type one error that cannot be discarded. However, no adjustments of type one error are planned because the goal of the trial is to detect any potential safety signals instead of confirming and investigating a safety concern.

The listings for the TEAEs resulting in death, Serious TEAEs and TEAEs of grade 3 or higher will be provided.

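### The post-hospital TEAE denominator keeps a subject who misses Month 4 only if they reported a late event, so the late-period rate tends to be slightly too high (minor)

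*SAP*

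**What the plan says.** SAP 5.1 analyses any-TEAE occurrence overall and by several breakdowns, one of which is period: in hospital, or from end of hospitalisation to Month 4. Events are assigned to a period by start date. The period 1 denominator is everyone who took at least one tablet. The period 2 denominator is "the number of subjects attending the 4-month visit or having reported a TEAE during the second period". Protocol 10.7.1 agrees: "the number of subjects attending the 4-month visit or have reported a TEAE during the second time period".

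The overall 4-month rate is divided by the whole Safety Set. For the interval, "The 95% confidence interval (CI) of the excess rate will be calculated using Wilson score interval". For the test, "A Cochran Mantel-Haenszel test stratified on the site of investigation will be used to compare the occurrence rate of both treatment groups".

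Three other provisions bear on who misses Month 4 and what is known about them:

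- **Withdrawal.** Protocol 3.1: "Any subject with a positive parasitological test result during the study will end their participation in the study". Protocol 8.3.2 says that these tests "will be conducted during screening period, at Month 1, and at the EoS visit at Month 4".
- **AE collection.** Protocol 8.5.4: "each trial subject will be questioned about the occurrence of AEs during hospitalisation period and study follow-up visits". Spontaneous reports are also recorded, and there are investigator contacts at Months 2 and 3.
- **Attrition.** Protocol 9.2 calls loss to follow-up low and gives no percentage. Protocol 7.7.1 mentions 8 replaced subjects. SAP 4.1 and Protocol 10.3 will show completion and discontinuation by treatment group.

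**The concern.** Take two subjects who leave after Month 1. One reported a headache at that visit and stays in the period 2 numerator and denominator. The other reported nothing and is removed from the denominator. Whether a leaver counts is decided by the outcome being measured.

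The plan gives this split a job. Protocol 10.7.1 uses it to interpret early and late events separately, and SAP 5.1 uses it to check that late events are not hidden among all events. Excess rates and NNTs are to be reported by period. If the arms lose different proportions, the distortion does not cancel between them.

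No planned analysis corrects the rate. The Kaplan-Meier and log-rank analyses follow time to a TEAE from dosing, so after discharge they inform only on subjects with no in-hospital TEAE, a narrower group. The planned sensitivity analysis in SAP 5.1 concerns treatment misallocation.

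**Working it through.** The documents state no late-period rate and no bias, so there is no figure of the plan's own to reproduce.

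**Inputs from the documents.** 900 acoziborole and 300 placebo (SAP 2.4.1). Period 2 is taken as Day 5 to Day 121, so T = 116 days (SAP 2.7.2). Month 1 is Day 31, which is 26 days into period 2. The only attrition count is 8 replaced subjects: 8/1200 = 0.67%, a floor.

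**Assumptions.** Attrition a = 0.67%, 2% and 5%. Late risk p = 2%, 30% and 40%. The 2% is borrowed from SAP 2.4.3 ("Excess rate of 1% (acoziborole = 2% of AEs of interest, Placebo = 1%) for safety purposes"), where it is not specific to period 2. The 30% and 40% are illustrative and have no source in the documents. Dropout is unrelated to risk, and the hazard is constant: h = -ln(1-p)/T.

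**Step 1: direction.** Let q be the proportion of leavers with a recorded late TEAE.

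Plan's rate = [(1-a)p + aq] / [(1-a) + aq]

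Bias = plan's rate - p = aq(1-p) / [(1-a) + aq]

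This is zero if q = 0 and positive otherwise.

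**Step 2: range of q.**

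- Low end (AEs recorded at visits only, uniform dropout times): q = (1 - 26/116) × [1 - exp(-26h)].
- Middle (all events before leaving recorded, uniform dropout times): q = 1 - p/[-ln(1-p)].
- Bound (leavers report the full-period risk): q = p.

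| p | visits only | full reporting | q = p |
|---|---|---|---|
| 2% | 0.0035 | 0.010 | 0.02 |
| 30% | 0.060 | 0.159 | 0.30 |
| 40% | 0.084 | 0.217 | 0.40 |

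**Step 3: bias in one arm's late rate (points), in the same order.** Example: a = 5%, p = q = 30% gives (0.285 + 0.015)/(0.95 + 0.015) = 0.300/0.965 = 31.09%, a bias of +1.09.

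| p | a = 0.67% | a = 2% | a = 5% |
|---|---|---|---|
| 2% | 0.00 / 0.01 / 0.01 | 0.01 / 0.02 / 0.04 | 0.02 / 0.05 / 0.10 |
| 30% | 0.03 / 0.07 / 0.14 | 0.09 / 0.23 / 0.43 | 0.22 / 0.58 / 1.09 |
| 40% | 0.03 / 0.09 / 0.16 | 0.10 / 0.26 / 0.49 | 0.26 / 0.68 / 1.24 |

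Uniform dropout is not the worst case. If leavers go just after a Month 3 contact (taken as Day 91) with full reporting, the bias at 5% attrition is +0.85 (p = 30%) to +0.98 (p = 40%).

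**Step 4: excess rate, equal true risks, attrition 2% in one arm and 5% in the other.** Size of shift (points), same order: 0.01 / 0.03 / 0.06 at 2% risk, 0.13 / 0.35 / 0.66 at 30%, 0.16 / 0.41 / 0.75 at 40%. It is negative if placebo loses more and positive if acoziborole does. With equal attrition and equal risks it is zero. The standard error, sqrt[p(1-p)(1/900 + 1/300)], is 0.93, 3.06 and 3.27 points.

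**Step 5: NNT.** Take true risks of 35% v 30% (excess 5 points, NNT 20.0) and q = p, so the plan's rate is p/[1 - a(1-p)]. With attrition 2% v 5% (acoziborole v placebo): 0.350/0.987 - 0.300/0.965 = 35.46% - 31.09% = 4.37 points, NNT 22.9. With 5% v 2%: 0.350/0.9675 - 0.300/0.986 = 36.18% - 30.43% = 5.75 points, NNT 17.4.

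**Step 6: the obvious alternative.** The same numerator over everyone in the study at discharge has bias -a(p-q). At 5% attrition with uniform dropout this runs from -0.05 × (0.30 - 0.159) = -0.71 to -0.05 × (0.40 - 0.084) = -1.58 points.

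**The case against.** The case for leaving the rule alone is a fair one.

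- **It is small.** At 2% attrition even the q = p bound is 0.49 points, about 0.15 of the standard error of the excess rate (0.49/3.27). It touches one breakdown of an unadjusted signal-detection analysis. This stands, and it is why the point is minor.
- **Readers will see attrition by arm** in the disposition tables, so they can judge or bound the effect. This also stands, although it does not correct the rate.
- **The rule discards no reported safety event**, and under uniform dropout it is closer to the truth than a crude fixed denominator: at 5% attrition and 30% risk, +0.58 v -0.71 points with full reporting, or +0.22 v -1.20 with visits only. This stands against that alternative but not against Kaplan-Meier. Conservatism within an arm also does not carry over to the difference between arms.
- **The late period carries less weight for attribution.** Protocol 3.3 reports that 97.7% of related TEAEs in the pivotal study came within 5 days of dosing. This stands.

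A reader might infer more than the documents support:

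- **That the primary result is inflated.** It is not, because its denominator is the whole Safety Set.
- **That withdrawal for positive parasitology depletes placebo and hides late harm.** After dosing, parasitology is scheduled only at Months 1 and 4, and a subject positive at Month 4 has attended Month 4. Only Month 1 or unscheduled positives can act this way. The documents give no numbers by arm, so neither the size nor the sign is known.
- **That the rule always overstates late risk.** This holds only if dropout is unrelated to risk. If leavers are at higher risk and their events go unrecorded, the rate can be too low.

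**Conclusion.** The concern holds as a minor flaw. Both documents make inclusion in the period 2 denominator depend on the outcome. With dropout unrelated to risk, the late-period rate is biased upward or not at all. The by-period excess rate and NNT can shift in either direction if attrition differs by arm.

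At the low attrition that the protocol describes, the bias is a fraction of a point. It passes one point only near 5% attrition, with a late risk of 30% or more and leavers reporting close to the full-period risk. The largest excess-rate shift shown, 0.75 points, is 0.23 of its standard error (0.75/3.27).

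These sizes rest on assumed late risks and attrition and on a constant hazard. The direction rests only on the wording of the rule and on dropout being unrelated to risk.

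**What to change.** In SAP 5.1, for the period 2 any-TEAE comparison:

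1. Define the risk set as all Safety Set subjects still in the study at end of hospitalisation.
2. Estimate the risk to Day 121 in each arm by Kaplan-Meier restarted at discharge. Censor event-free leavers at the last visit or contact at which AEs were ascertained.
3. Derive the period 2 excess rate and NNT from these estimates, with a standard Greenwood-based interval.
4. Keep the current crude rate as a sensitivity analysis.

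Do not rely on the crude rate over the fixed denominator alone, because it errs downward (Step 6). The overall analysis needs no change.

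Amend Protocol 10.7.1 to match, or record the change as a deviation in the study report under Protocol 10.11.

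**Cost.** A short SAP paragraph and slightly more programming, with no new data. Period 2 would use a different interval method from the Wilson interval of the overall analysis. The estimate still assumes that dropout is unrelated to TEAE risk.

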The time course of treatment effect will be analysed using the log rank test stratified by study centre and will be performed on the time to occurrence of TEAEs, taking into account the attrition rate of subjects who are being followed up. A loss to follow-up or a withdrawal will be censored at the time of the last attended visit. The Kaplan-Meier estimates of the proportion of subjects without any TEAE in each treatment group will be presented graphically to assess the time course of the response. The rate of occurrence of AEs will be analysed by the true positive status (subjects with parasites detected during the follow up period) in either treatment or placebo groups.
Secondary endpoint analysis The secondary endpoints are the occurrence of AEs from the time that subjects provide written informed consent to the EoS and changes from baseline in ECG and laboratory safety test results (biochemistry and haematology) to the EoS. The majority of measured parameters are quantitative and the change from baseline will be the difference between two values. For parameters with binary outcomes (presence or absence), contingency tables (before versus after treatment) will describe the change (or not) of status.
Exploratory endpoint analysis
The occurrence rate of positive extravascular dermal T.b. gambiense at 4 months based on the primary diagnostic parameters will be the primary measure of interest because the sample size is known and it corresponds to a measure of the level of potential transmission of reservoirs. The magnitude of the treatment effect will be the odds ratio (OR) of positive dermal T.b. gambiense. As the OR is not easy to interpret when the rate of positive subjects in the placebo group is not small (P0 >0.05), the OR will be converted into the risk ratio (RR) using the following formula: RR = (P1/P0) = OR/[(1-P0) + (P0×OR)], where P1 and P0 are the estimated proportions of positive subjects in the acoziborole arm and placebo arm respectively. The ER (P1 – P0) will also be estimated as a secondary measure of the magnitude of the treatment as well as the NTT (number of subjects needed to treat to get one less positive subject at 4 months in acoziborole group). Interim analysis

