QTcCorrected QT intervalRDTRapid Diagnostic TestRRRisk RatioSAPStatistical Analysis PlanSASStatistical Analysis SystemSHERLOCKSpecific High-sensitivity Enzymatic Reporter unLOCKing	QQ	Quantile-Quantile
RDTRapid Diagnostic TestRRRisk RatioSAPStatistical Analysis PlanSASStatistical Analysis SystemSHERLOCKSpecific High-sensitivity Enzymatic Reporter unLOCKing	RT-qPCR	Quantitative Reverse Transcription PCR
RRRisk RatioSAPStatistical Analysis PlanSASStatistical Analysis SystemSHERLOCKSpecific High-sensitivity Enzymatic Reporter unLOCKing	QTc	Corrected QT interval
SAPStatistical Analysis PlanSASStatistical Analysis SystemSHERLOCKSpecific High-sensitivity Enzymatic Reporter unLOCKing	RDT	Rapid Diagnostic Test
SASStatistical Analysis SystemSHERLOCKSpecific High-sensitivity Enzymatic Reporter unLOCKing	RR	Risk Ratio
SHERLOCK Specific High-sensitivity Enzymatic Reporter unLOCKing	SAP	Statistical Analysis Plan
	SAS	Statistical Analysis System
SOC System Organ Class	SHERLOCK	Specific High-sensitivity Enzymatic Reporter unLOCKing
	SOC	System Organ Class

TEAE	Treatment Emergent Adverse Event
TLF	Tables Listings and Figures
WHO	World Health Organization
WMW	Wilcoxon-Mann-Whitney

1. Introduction

This Statistical Analysis Plan (SAP) describes the statistical analysis methods and data presentations for the DNDi-OXA-04-HAT study. This SAP is based on the Study Protocol version 3.0, dated 13 June 2023. International Conference on Harmonization of Technical Requirements for Registration of Pharmaceuticals for Human Use (ICH): *Guidance on Statistical Principles in Clinical Trials*¹ and the ICH E3 Guideline: *Structure and Content of Clinical Study Reports*² were used as a guide for the preparation of this SAP. Additional analysis not described in the SAP but deemed necessary will be clearly described as a post-hoc analysis in the Clinical Study Report (CSR).

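### SAP 5.1 makes treatment group a stratum of the time-to-TEAE log-rank test, so the test as written cannot compare acoziborole with placebo and departs from the protocol.

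*SAP*

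**What the plan says.** SAP 5.1 plans "a log rank test stratified by site and treatment group on the time to occurrence of TEAEs", with its result to be shown on the Kaplan-Meier figure. The next description in that paragraph is "Kaplan Meier estimates of the proportion of subjects without any TEAE will be presented graphically", with no mention of arm.

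The protocol differs on both points. In 10.7.1 the time course of treatment effect "will be analysed using the log rank test stratified by study centre", and the protocol summary says the same: "The time course of treatment effect will be analysed using the log rank test stratified by study centre". Its Kaplan-Meier sentence in 10.7.1 is explicit about arm: "The Kaplan-Meier estimates of the proportion of subjects without any TEAE in each treatment group will be presented graphically".

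The SAP introduction states: "This SAP is based on the Study Protocol version 3.0, dated 13 June 2023". That is the version in hand, and the SAP neither announces nor explains a change to this test. The companion analysis in the same SAP section has the usual form: "A Cochran Mantel-Haenszel test stratified on the site of investigation will be used to compare the occurrence rate of both treatment groups".

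**The concern.** In a stratified log-rank test, the stratifying factors are held fixed and the factor of interest is compared within each stratum. SAP 5.1 lists treatment among the factors held fixed, which leaves nothing to compare.

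This is the only formal time-to-event test under the primary objective. It is also the between-arm TEAE test meant to allow for attrition; the Cochran-Mantel-Haenszel test compares simple occurrence rates. Protocol 10.7.1 wants early events, thought more likely to reflect treatment, read separately from late ones, so timing matters here.

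As the text stands, a programmer must depart from the SAP to produce the planned output. The SAP introduction says analyses it does not describe will be labelled post hoc, and Protocol 10.11 requires deviations to be justified in the study report. Read literally, the protocol's own valid test could end up reported as a departure.

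**Working it through.** **No plan figure to reproduce.** Neither document gives an event count, hazard ratio or power for this test. The check is algebraic, with a simulation as illustration.

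**Inputs from the documents:** 900 acoziborole and 300 placebo subjects (Protocol 10.1.1, SAP 2.4.1); two-sided 5% level (SAP 3.1); month-4 visit at day 121 (Protocol Table 2).

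**Formulas.** At each event time in a stratum, let n be the number at risk, n1 those at risk on acoziborole, d the events and d1 the events on acoziborole. Summing over event times and strata:

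- U = Σ (d1 − d·n1/n)
- V = Σ d·(n1/n)·(1 − n1/n)·(n − d)/(n − 1)
- chi-square = U²/V on 1 df

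**Strata = site × treatment (SAP 5.1 as written)**

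- Acoziborole stratum: n1 = n and d1 = d, so the U term is d − d = 0 and the V term contains (1)(1 − 1) = 0.
- Placebo stratum: n1 = 0 and d1 = 0, so the U term is 0 − 0 = 0 and the V term contains (0)(1 − 0) = 0.
- Hence U = 0 and V = 0 in any data set, and the chi-square is 0/0.

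**One risk set in numbers.** Assume 10 equal sites, giving 900/10 = 90 and 300/10 = 30 subjects per site, all still at risk, and one event on acoziborole.

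- Site strata: expected = 1 × 90/120 = 0.75; contribution to U = 1 − 0.75 = 0.25; contribution to V = 1 × 0.75 × 0.25 × 119/119 = 0.1875.
- Site × treatment strata: expected = 1 × 90/90 = 1; contribution to U = 0; contribution to V = 1 × 1 × 0 = 0.

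**Simulation.** Assumptions not taken from the documents: 10 sites of about equal size, 40% placebo TEAE risk by day 121, exponential onset times, hazard ratio 1, 1.5 or 3, and 200 replicates each. The U, V and chi-square columns come from one data set per row.

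| Hazard ratio | Site strata: U | V | Chi-square | Site × treatment: U, V | Rejection rate, site strata (200 replicates) |
|---|---|---|---|---|---|
| 1 | −9.67 | 83.80 | 1.12 | 0, 0 | 6.5% |
| 1.5 | 33.78 | 115.06 | 9.92 | 0, 0 | 99.5% |
| 3 | 167.38 | 172.78 | 162.1 | 0, 0 | 100% |

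For example, at hazard ratio 1.5, 33.78²/115.06 = 9.92.

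**Second set.** Twelve single trials of 1200 subjects (3:1) used 4, 8 or 12 sites and assumed 4-month risks of 50% v 50%, 50% v 40%, 60% v 30% or 90% v 10%. The SAP version gave U = 0 and V = 0 in all 12. In the most extreme case (90% v 10%, 4 sites) it gave 821 observed and 821 expected events on acoziborole. The site-stratified chi-squares at 4 sites were 0.15, 10.99, 78.55 and 551.04 in the order listed.

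**The case against.** The best reply is that everyone can see what was meant. The SAP sentence opens by naming a treatment effect as its target, the parent protocol is unambiguous, and the neighbouring Cochran-Mantel-Haenszel test is set up correctly. The phrase may be loose usage for the two variables entered in the test. The table and figure shells are attached separately and were not available, so they may already show this output by arm. A 0/0 result would be noticed at once, no decision rule or multiplicity control hangs on the test, and simulation adds nothing to a one-line identity.

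Much of this stands. The intent is recoverable, the consequence is limited, and the simulated chi-squares only illustrate the algebra; they say nothing about the size of effect in this trial.

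It does not rescue the sentence. Within the test specification, treatment appears only as a stratifier, and the Kaplan-Meier sentence has lost its reference to arm, so the paragraph does not correct itself. Nor is failure certain to be visible. Someone who took the site-by-arm cells as the groups to be compared would obtain a p-value; with 10 sites that is a test on 10 × 2 − 1 = 19 df, mixing site differences with the treatment difference. That is not the protocol's test either.

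**Conclusion.** The concern holds. SAP 5.1 conflicts with the protocol on which it is based, and with treatment as a stratum the planned between-arm log-rank test does not exist. This follows from the algebra and needs no assumption about event rates or number of sites. The one premise is that the stratifying factors are read in the ordinary sense.

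The wording is probably a slip, and its reach is short: the excess rate and its confidence interval, the NNT, the site-stratified Cochran-Mantel-Haenszel test and the period tables do not depend on it, nor does any sample-size figure. Kaplan-Meier curves by arm can still be computed, though the SAP no longer says they will be. It should be corrected because it is an operative analysis rule that cannot be carried out as written.

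**What to change.** In SAP 5.1, specify a log-rank test that compares the treatment groups and is stratified by site only, and put back the statement that the Kaplan-Meier estimates are shown for each arm. Both edits restore Protocol 10.7.1 and add no new analytic choice. The same edit could usefully say whether the rule pooling sites with fewer than 100 subjects, which SAP 5.1 gives with the odds-ratio homogeneity test, also defines the log-rank strata.

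The cost is two phrases in the SAP and the matching program specification. SAP 3.4.4 speaks of unblinding as still to come, so the correction belongs before that step. There is no statistical downside.
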